10.12.2 Children's dermatology life quality index (C-DLQI)

| CHILDREN'S DERMATOLOGY LIFE QUALITY INDEX | | | |
|---|---|--|--|
| Hospital No | Diagnosis: | CDLQI SCORE: | |
| Name: | | | |
| Age: | | | |
| Address: | Date: | | |
| The aim of this questionnaire is to measure how much your skin problem has affected you OVER THE LAST WEEK. Please tick  one box for each question. | | | |
| 1. Over the last week, how itchy, "scratchy", sore or painful has your skin been? | Very much Quite a lot Only a little Not at all |     | |
| 2. Over the last week, how embarrassed or self conscious, upset or sad have you been because of your skin? | Very much Quite a lot Only a little Not at all |     | |
| 3. Over the last week, how much has your skin affected your friendships? | Very much Quite a lot Only a little Not at all |     | |
| 4. Over the last week, how much have you changed or worn different or special clothes/shoes because of your skin? | Very much Quite a lot Only a little Not at all |     | |
| 5. Over the last week, how much has your skin trouble affected going out, playing, or doing hobbies? | Very much Quite a lot Only a little Not at all |     | |
| 6. Over the last week, how much have you avoided swimming or other sports because of your skin trouble? | Very much Quite a lot Only a little Not at all |     | |
| 7. Last week ,  was it school time?  If school time: Over the last week, how much did your skin problem affect your school work? | Prevented school Very much Quite a lot Only a little Not at all |     | |
| OR | | | |
| was it holiday time?  If holiday time: How much over the last week, has your skin problem interfered with your enjoyment of the holiday? | Very much Quite a lot Only a little Not at all |     | |
| 8. Over the last week, how much trouble have you had because of your skin with other people calling you names, teasing, bullying, asking questions or avoiding you? | Very much Quite a lot Only a little Not at all |     | |
| 9. Over the last week, how much has your sleep been affected by your skin problem? | Very much Quite a lot Only a little Not at all |     | |
| 10. Over the last week, how much of a problem has the treatment for your skin been? | Very much Quite a lot Only a little Not at all |     | |
| Please check that you have answered EVERY question. Thank you. | | | |
| ©M.S. Lewis-Jones, A.Y. Finlay, May 1993. This must not be copied without the permission of the authors. | | | |

10.12.3 Infants' Dermatitis Quality of Life Index (IDQOL)

| Draft 7 | | INFANTS' DERMATITIS QUALITY OF LIFE INDEX (IDQOL) | |
|--|-------|--|--------------------------|
| Name: | Date: | IDQOL SCORE |  |
| The aim of this chart is to record how your child's dermatitis has been. Each question concerns THE LAST WEEK ONLY. Please could you answer every question. | | | |
| Dermatitis Severity | | | |
| Over the last week, how severe do you think your child's dermatitis has been?; i.e. how red, scaly, inflamed or widespread. | | Extremely severe |  |
| | | Severe |  |
| | | Average |  |
| | | Fairly good |  |
| | | None |  |
| Life Quality Index | | | |
| 1. Over the last week, how much has your child been itching and scratching ? | | All the time |  |
| | | A lot |  |
| | | A little |  |
| | | None |  |
| 2. Over the last week, what has your child's mood been? | | Always crying, extremely difficult |  |
| | | Very fretful |  |
| | | Slightly fretful |  |
| | | Happy |  |
| 3. Over the last week approximately how much time on average has it taken to get your child off to sleep each night? | | More than 2 hrs |  |
| | | 1 - 2 hrs |  |
| | | 15mins - 1 hr |  |
| | | 0-15mins |  |
| 4. Over the last week, what was the total time that your child's sleep was disturbed on average each night? | | 5 hrs or more |  |
| | | 3 - 4 hrs |  |
| | | 1 - 2 hrs |  |
| | | Less than 1 hour |  |
| 5. Over the last week, has your child's eczema interfered with playing or swimming ? | | Very much |  |
| | | A lot |  |
| | | A little |  |
| | | Not at all |  |
| 6. Over the last week, has your child's eczema interfered with your child taking part in or enjoying other family activities ? | | Very much |  |
| | | A lot |  |
| | | A little |  |
| | | Not at all |  |
| 7. Over the last week, have there been problems with your child at mealtimes because of the eczema? | | Very much |  |
| | | A lot |  |
| | | A little |  |
| | | None |  |
| 8. Over the last week, have there been problems with your child caused by the treatment ? | | Very much |  |
| | | A lot |  |
| | | A little |  |
| | | None |  |
| 9. Over the last week, has your child's eczema meant that dressing and undressing the child has been uncomfortable ? | | Very much |  |
| | | A lot |  |
| | | A little |  |
| | | None |  |
| 10. Over the last week how much has your child having eczema been a problem at bathtime ? | | Very much |  |
| | | A lot |  |
| | | A little |  |
| | | None |  |
| Please can you check that you have answered every question. <small>© M.S. Lewis-Jones, A.Y. Finlay Jan 2000</small> | | | |

10.13 APPENDIX 13: ABBREVIATIONS

| | |
|-------------------|---|
| AD: | atopic dermatitis |
| ADA: | anti-drug antibody |
| ADL: | activities of daily living |
| ADRs: | adverse drug reactions |
| AEs: | adverse events |
| AESI: | adverse event of special interest |
| ALT: | alanine aminotransferase |
| C-DLQI: | children's dermatology life quality index |
| CFR: | Code of Federal Regulation |
| CI: | confidence interval |
| Cmax: | maximum serum concentration observed |
| COVID-19: | coronavirus disease-2019 |
| CRSwNP: | chronic rhinosinusitis with nasal polyposis |
| CSR: | clinical study report |
| CSU: | chronic spontaneous urticaria |
| CV: | coefficient of variation |
| DTP: | direct-to-patient |
| ECG: | electrocardiogram |
| eCRF: | electronic case report form |
| EOS: | end of study |
| EOT: | end of treatment |
| E-R: | exposure-response |
| EU: | European Union |
| Fc ϵ RI: | Fc gamma receptor |
| GDPR: | general data protection regulation |
| HBsAb: | hepatitis B surface antibody |
| HBsAg: | hepatitis B surface antigen |
| HCV RNA: | hepatitis C virus ribonucleic acid |
| HCVAb: | hepatitis C virus antibody |
| HIV: | human immunodeficiency virus |
| HRQoL: | health-related quality of life |
| HSS: | hive severity score |
| HSS7: | hive severity score over 7 days |
| IAF: | informed assent form |
| IB: | Investigator's Brochure |
| ICF: | informed consent form |
| IDQOL: | infant's dermatitis quality of life index |
| IEC: | Independent Ethics Committee |
| IgE: | immunoglobulin E |
| IL: | interleukin |
| IL-4R α : | interleukin-4 receptor alpha |
| IMP: | investigational medicinal product |
| IRB: | Institutional Review Board |

| | |
|-------------|---|
| IRT: | interactive response technology |
| ISS: | itch severity score |
| ISS7: | Itch Severity Score over 7 days |
| ITT: | intent-to-treat |
| IVIG: | intravenous immunoglobulin |
| IVRS: | interactive voice response system |
| IWRS: | interactive web response system |
| mAb: | monoclonal antibody |
| mUAS: | modified urticaria activity score |
| NIMP: | noninvestigational product |
| OCS: | oral corticosteroids |
| PCSA: | potentially clinically significant abnormality |
| PK: | pharmacokinetics |
| PRO: | patient reported outcome |
| Q2W: | every 2 weeks |
| Q4W: | every 4 weeks |
| QoL: | quality of life |
| SAEs: | serious adverse events |
| SAP: | statistical analysis plan |
| SARS-CoV-2: | severe acute respiratory syndrome-coronavirus 2 |
| SC: | subcutaneously |
| SD: | standard deviation |
| SEM: | standard error of the mean |
| SoA: | schedule of activities |
| SUSAR: | suspected unexpected serious adverse reaction |
| TB: | tuberculosis |
| TBV: | total blood volume |
| TEAEs: | treatment emergent adverse events |
| UAS: | urticaria activity score |
| UAS7: | urticaria activity score over 7 days |
| ULN: | upper limit of normal |
| US: | United States |
| V2: | visit 2 |
| WOCBP: | woman of childbearing potential |

10.14 APPENDIX 14: PROTOCOL AMENDMENT HISTORY

Not applicable.

1 INTRODUCTION

1.1 STUDY DESIGN

This is a Phase 3, multicenter, single-arm, 24-week treatment study assessing the PK and safety of dupilumab in participants ≥ 2 years to < 12 years of age with CSU not adequately controlled with H1-antihistamine treatment.

The primary objective of this study is to characterize the PK profile and the secondary objective is to assess the safety profile of dupilumab in children aged ≥ 2 years to < 12 years with uncontrolled CSU. This study will additionally collect clinical information regarding the response to treatment in this age group, however all efficacy analyses will be descriptive.

In this study, all enrolled participants will receive dupilumab injections in a weight/age-tiered dosing regimen for 24 weeks, followed by a 12-week post-treatment observational period at the end of the study intervention.

The study consists of 3 periods:

- Screening period (2 to 4 weeks)
- Study intervention period (24 weeks)
- Follow-up period (12 weeks)

The Sponsor estimates that drug concentrations in serum (primary endpoint) can be adequately assessed with approximately 24 enrolled participants with ≥ 8 CSU participants in each of the 2 weight groups (≥ 5 kg to < 30 kg and ≥ 30 kg to < 60 kg). It is expected that a minimum of 8 participants per weight group and a total of 24 participants are sufficient and adequate to perform PK analysis.

All participants will be administered dupilumab subcutaneously (SC) at one of 4 dose regimens based on the body weight and age at the screening visit:

Table 1 - Dosing Regimen in the Study

Body weight	Age	Loading Dose (LD)	Dose regimen
5 kg to < 15 kg	NA	NA	200 mg Q4W
15 kg to < 30 kg	≥ 2 to < 6 years	NA	300 mg Q4W
15 kg to < 30 kg	≥ 6 to < 12 years	600 mg	300 mg Q4W
30 kg to < 60 kg	NA	400 mg	200 mg Q2W

LD=Loading dose; Q2W=Every 2 weeks; Q4W=Every 4 weeks; NA: Not Applicable

All participants will complete a 12-week post-treatment period (Follow-up period) without study intervention after completing their treatment period.

1.2 OBJECTIVES AND ENDPOINTS

Table 2 - Objectives and endpoints

Objectives	Endpoints
Primary 
• To characterize the serum concentration of dupilumab over time.	
• Concentration of dupilumab in serum over time including C_{trough} at Week 12 and Week 24.
Secondary 
• To assess the safety of dupilumab.• To assess the immunogenicity of dupilumab.• To evaluate the improvement in health-related Quality of Life (QoL) in participants with CSU receiving dupilumab who remain symptomatic despite the use of H1-antihistamine.• To assess the impact of dupilumab on urticaria activity, itch and hives severity scores in participants with CSU who remain symptomatic despite the use of H1-antihistamine.	
• Safety and tolerability assessments: Incidence of TEAEs or SAEs.• Incidence of ADA to dupilumab over time.• Change from baseline in Children's Dermatology Life Quality Index (C-DLQI) in children from 4 years to less than 12 years of age at Week 24.• Change from baseline in Infant's Dermatitis Quality of Life Index (IDQOL) in children from 2 years to less than 4 years of age at Week 24.• Change from baseline in the modified Urticaria Activity Score over 7 days (mUAS7) at Week 24.• Change from baseline in the Itch Severity Score over 7 days (ISS7) at Week 24.• Change from baseline in the Hive Severity Score over 7 days (HSS7) at Week 24.

1.2.1 Estimands

There are no estimands for the study. All efficacy endpoints are descriptive.

2 ANALYSIS POPULATIONS

The following populations for analyses are defined:

Table 3 - Populations for analyses

Population	Description
Screened	All participants who signed the ICF.
Enrolled	All participants from the screened population who have been allocated to an intervention regardless of whether the intervention was received or not.
Exposed	All screened participants who have taken at least one dose of study intervention regardless of the amount of study intervention administered.
Intent-to-treat (ITT)	All enrolled participants. Participants will be analyzed according to the intervention they were allocated to.
Population without trial impact (disruption) due to COVID-19	All enrolled participants: 
without any critical or major deviation related to COVID-19,and who did not permanently discontinue treatment due to COVID-19,and who did not permanently discontinue the study due to COVID-19.
Safety	All enrolled participants who have taken at least one dose of study intervention, regardless of the amount of intervention administered. Participants will be analyzed according to the intervention they actually received.
Pharmacokinetic (PK)	All enrolled and treated participants (safety population) with at least one post-baseline PK result. Participants will be analyzed according to the intervention they actually received.
ADA	All enrolled participants treated with dupilumab with at least one post-baseline ADA result (positive, negative or inconclusive). Participants will be analyzed according to the intervention they actually received.

Participants exposed to study intervention before or without being enrolled will not be considered enrolled. The safety experience of these participants will be reported separately.

Enrolled participants for whom it is unclear whether they received the study intervention will be considered as exposed and will be included in the safety population.

For any participant enrolled more than once, only the data associated with the first enrollment will be used in any analysis population. The safety experience associated with any later enrollment will be reported separately.

If >10% participants are impacted by the COVID-19 pandemic, additional summaries by COVID-19 subgroups will be provided. Participants impacted by the COVID-19 pandemic are defined as enrolled participants with any critical or major deviation related to COVID-19 or who permanently discontinued study intervention or study due to COVID-19.

3 STATISTICAL ANALYSES

3.1 GENERAL CONSIDERATIONS

In general, continuous data will be summarized using the number of observations available, mean, standard deviation (SD), median, Q1, Q3, minimum, and maximum. Categorical and ordinal data will be summarized using the count and percentage of participants.

The baseline value is defined as the last available value before the first dose of IMP administration except for efficacy analysis, for which the baseline is defined in [Section 3.3.1.1](#) and [Section 3.3.1.2](#). For participants enrolled but not treated, the baseline value is defined as the last available value before enrollment.

Observation period

The observation period will be divided into 4 segments:

- The **pre-treatment** period is defined as the period up to first IMP administration.
- The **treatment-emergent (TE) period** is defined as the period from the first IMP administration to the last IMP administration +98 days (+112 days for children <30 kg). The treatment-emergent period includes the following 2 periods:
 - The **on-treatment period** is defined as the period from the first IMP administration to the last administration of the IMP +14 days (+28 days for children <30 kg),
 - The **residual treatment period** is defined as the period from the end of the on-treatment period to the end of the treatment-emergent period.
- The **post-treatment period** is defined as the period from the end of the treatment-emergent period.

Unless otherwise specified, analyses will be performed overall and by intervention group:

- 200 mg Q4W
- 300 mg Q4W
- 300 mg Q4W, 600 mg LD
- 200 mg Q2W, 400 mg LD

With the footnote: LD = Loading Dose; Q2W = Every 2 weeks; Q4W = Every 4 weeks.

3.2 PRIMARY ENDPOINT(S) ANALYSIS

Serum concentrations of dupilumab including C_{trough} at Week 12 and Week 24 will be summarized in the PK population using arithmetic and geometric means, SD, SEM, CV, minimum, median, and maximum per sampling time. Summary statistics may also be performed by weight or dose subgroup, if the number of participants in each subgroup allows it.

If date and/or time of the drug injection and/or sampling is missing then the concentration will not be taken into account. For treated participants and post-treatment time points, where concentration

values are below the lower limit of quantification (LLOQ), one-half of the LLOQ will be used in listings, graphic representations and summary statistics. The pre-dose concentration value at Week 0 will be used as 0 if the pre-dose concentration values at Week 0 are below the lower limit of quantitation. Values will be expressed in the tables with no more than three significant figures. All concentrations below the LLOQ and missing data will be labelled as such in the concentration data listings.

3.3 SECONDARY ENDPOINT(S) ANALYSIS

The secondary endpoints detailed in this section are efficacy endpoints.

Other secondary endpoints analyses are defined in [Section 3.5.2](#) for AEs, and [Section 3.6.1.1](#) for ADA analyses.

3.3.1 Efficacy analysis

The efficacy analysis will be conducted on the ITT population. Continuous efficacy secondary endpoints will be summarized using descriptive statistics (number of observations available, mean and the corresponding 95% CI, SD, median, minimum, and maximum).

3.3.1.1 C-DLQI and IDQOL

For participants from 4 years to less than 12 years of age:

C-DLQI items will be converted into numeric values as follows: 0=Not at all; 1=Only a little; 2=Quite a lot; 3=Very much (or "Prevented school" for item 7); for each timepoint. A global score of C-DLQI by timepoint will be computed by summing values of the 10 items.

For participants from 2 years to less than 4 years of age:

IDQOL items will be converted into numeric values for each timepoint as described in [Table 4](#):

Table 4 - Numeric conversion for IDQOL items

Question number	Question label	Item	Numeric value of item
-	Dermatitis Severity	Extremely severe	4
		Severe	3
		Average	2
		Fairly good	1
		None	0
1	Over the last week, how much has your child been itching and scratching?	All the time	3
		A lot	2
		A little	1
		None	0

Question number	Question label	Item	Numeric value of item
2	Over the last week, what has your child's mood been?	Always crying, extremely difficult	3
		Very fretful	2
		Slightly fretful	1
		Happy	0
3	Over the last week approximately how much time on average has it taken to get your child off to sleep each night?	More than 2 hours	3
		1 - 2 hours	2
		15mins - 1 hour	1
		0-15mins	0
4	Over the last week, what was the total time that your child's sleep was disturbed on average each night?	5 hours or more	3
		3 - 4 hours	2
		1 - 2 hours	1
		Less than 1 hour	0
5 to 10	-	Very much	3
		A lot	2
		A little	1
		Not at all/None	0

A global score of IDQOL by timepoint will be computed by summing values of the 10 life quality index items (dermatitis severity score is excluded from the calculation of the global score). Handling missing items from IDQOL will be same as for C-DLQI.

For both questionnaires, if one question is left unanswered this is scored 0 and the scores are summed and expressed as usual out of a maximum of 30. If two or more questions are left unanswered the questionnaire is not scored. If two or more response options are ticked for one question, the response option with the highest score should be recorded. Baseline is considered as the closest assessment to the first IMP administration on or prior to Day 1 but no later than Day 4.

Total scores and change from baseline will be summarized quantitatively for C-DLQI and IDQOL by timepoint. Raw scores and change from baseline of dermatitis severity assessed by IDQOL questionnaire will be summarized at Week 24.

3.3.1.2 Itch and Hive Severity Scores and Modified Urticaria Activity Score

For each daily assessment:

- Itch Severity Score items will be converted into numeric values as follows: 0=None; 1=Mild (present but not annoying or troublesome); 2=Moderate (troublesome but does not interfere with normal daily activity or sleep); 3=Intense (interferes with normal daily activity or sleep).

- Hive Severity Scores item will be converted into numeric values as follows:

Table 5 - Numeric values for Hives Severity Scores

Hives severity (number of hives)	Hives severity score
None	0
1-9	1
10-30	2
>30	3

The ISS7 and HSS7 baseline values are the sum of the 7 daily measurements obtained within the 7 days prior to first IMP administration. For subsequent visits, the sum of the 7 measurements on and prior to the target visit will be used (e.g., sum of days 163 through 169 for the visit at Week 24). Day ranges to be used for ISS7 and HSS7 derivations from Week 1 to Week 36 are described in [Section 5.6](#). ISS7 and HSS7 total scores and change from baseline will be summarized quantitatively by timepoint [from baseline to End of Study (EOS)].

Handling of missing daily score: if a participant has more than 50% of non-missing daily scores within 7 days prior to the visit for baseline; and on and prior for subsequent visits, (i.e. 4 or more non-missing scores) then the weekly score will be calculated as the sum of the available scores divided by the number of non-missing daily scores and multiplied by 7. Otherwise, the weekly score will be set to missing.

Additionally, mUAS7 will be computed by summing ISS7 and HSS7 scores. mUAS7 total score and change from baseline will be summarized quantitatively by timepoint.

If one of the ISS7 or HSS7 is missing, the mUAS7 will be set to missing.

mUAS7 total score will also be summarized in category as follows by timepoint:

- 0 = Itch and hive
- 1-6 = Well-controlled urticaria
- 7-15 = Mild urticaria
- 16-27 = Moderate activity urticaria
- 28-42 = Severe activity urticaria

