1.3 SCHEDULE OF ACTIVITIES (SOA)

| Procedure | Screening (14 to 28 days before Day 1) | Intervention Period (24 Weeks) | | | | | Follow-up (12 weeks) |
|---|--|--------------------------------|------|------|-------|---------|----------------------|
| | | Wk 0 (Day 1) | Wk 1 | Wk 2 | Wk 12 | Wk 24 | |
| Visit ^a | 1 | 2 | 3A | 3B | 4 | 5 (EOT) | 6 (EOS) |
| Screening | | | | | | | |
| Informed consent/assent ^b | X | | | | | | |
| Inclusion and exclusion criteria ^c | X | X | | | | | |
| Demographics | X | | | | | | |
| Medical history ^d | X | | | | | | |
| Prior and concomitant medications | X | X | X | X | X | X | X |
| Dispense e-diary/Participant and/or parents/caregiver e-diary training ^e | X | | | | | | |
| Study intervention | | | | | | | |
| IMP administration/ injection administration and observation training | | X ^{f, g} | | | | | |
| IRT attribution treatment | | X | | | X | | |
| Safety^h | | | | | | | |
| Full physical examination ⁱ | X | X | | | X | X | X |
| Vital signs ^j | X | X | | | X | X | X |
| 12-lead ECG ^k | X | | | | | X | X |
| AE reporting, including SAEs | <=====X=====> | | | | | | |
| Laboratory testing | | | | | | | |
| Hepatitis (HBsAg, HBsAb, HBcAb, HCVAb) and HIV Serology ^l | X | | | | | | |
| Pregnancy test: menstruating participants only ^m | Ser | Ur | | | Ur | Ur | Ur |
| Menstruation status | X | X | | | X | X | X |

| Procedure | Screening (14 to 28 days before Day 1) | Intervention Period (24 Weeks) | | | | | Follow-up (12 weeks) |
|--|--|--------------------------------|----------------|----------------|-------|---------|----------------------|
| | | Wk 0 (Day 1) | Wk 1 | Wk 2 | Wk 12 | Wk 24 | |
| Visit ^a | 1 | 2 | 3A | 3B | 4 | 5 (EOT) | 6 (EOS) |
| Hematology (including basophil/eosinophil counts), biochemistry, urine analysis ^{n,o} | X | | | | | X | |
| Participant's report outcome (PRO) | | | | | | | |
| Severity symptoms score questionnaires (PRO): modified UAS7, ISS7, and HSS7 | X ^p Modified UAS7 (includes ISS7 and HSS7 as components), once daily from Visit 1 to Visit 6 | | | | | | |
| QoL questionnaires ^q : C-DLQI and IDQOL | | X | | | | X | |
| Pharmacokinetics and ADA^r | | | | | | | |
| Serum PK samples for dupilumab concentration | | X | X ^s | X ^t | X | X | X |
| Anti-dupilumab antibody | | X | | | X | X | X |
| Biomarkers | | | | | | | |
| Serum Total IgE ^u | | | X | | | X | |

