Abbreviations: ADA = anti-drug antibodies; AEs = adverse events; AESI= adverse event of special interest; C-DLQI = Children's dermatology Life Quality Index; CRP = C-reactive protein; CSU = chronic spontaneous urticaria; ECG = electrocardiogram; eCRF = electronic case report form; E/D = early discontinuation; EOS = End of Study; EOT= End of Treatment; HBcAb = hepatitis B core antibody; HBsAb = hepatitis B surface antibody; HBsAg = hepatitis B surface antigen; HCVAb = hepatitis C virus antibody; HIV = Human Immunodeficiency Virus; HSS7 = hive severity score over 7 days; IDQOL = Infant's dermatitis quality of life index; IgG anti-TPO = immunoglobulin G anti-thyroperoxydase; Ig E = immunoglobulin E; IMP = investigational medicinal product; ISS7 = itch severity score over 7 days; PK = pharmacokinetic; Q2W = every 2 weeks; Q4W = every 4 weeks; PRO = patient report outcome; ; rtPCR = reverse transcription–polymerase chain reaction; SAE = serious adverse event; Ser = serum; TB = tuberculosis; UAS7 = urticaria activity score over 7 days; Ur = urine.

- a Allowed time window of ± 3 days for each visit of treatment period and ± 5 days for the Follow-up visit.
- b Prior to any screening assessments: all participants ≥ 6 years of age (or above an age determined by the Institutional Review Board [IRB]/Independent Ethics Committee [IEC]) and their parent(s)/caregiver(s)/legal guardian(s) will receive information about the study, on study objective(s) and procedures, to the fullest extent possible, in their language and in terms they are able to understand, and must sign and date the IRB/IEC approved Informed Assent Form (IAF) and Informed Consent Form (ICF), respectively.
- c The clinical status of the participant should be rechecked before first dose of study intervention.
- d Medical history, allergic comorbidities history.
- e Training of participants and parents/caregiver regarding completion of diary to record (a) administration of each dose of drug outside the clinic by parent/caregiver for participants; (b) completion of the assessment of participant reported questionnaires for participants aged ≥ 2 years to <12 years.

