5.4 APPENDIX 4 DATA HANDLING CONVENTIONS

Analysis windows for time points

Unless stated otherwise, the following analysis windows ([Table 10](#), [Table 11](#), and [Table 12](#)) will decide how the post-baseline scheduled and/or unscheduled visits will be used in the by-visit analyses of efficacy, safety, biomarker and ADA variables.

A measurement (scheduled or unscheduled) will be used if it is available and measurement date is within the analysis window.

After applying these time windows, if multiple assessments are associated with the same time point, the closest from the targeted study day will be used. If the difference is a tie, the value after the targeted study day will be used. If multiple valid values exist within a same day, then the first value of the day will be selected.

If there is no measurement for a given parameter in an analysis window, data will be considered missing for the corresponding visit.

Table 10 - Analyses window definition for participants assigned to PK - Schedule A

Scheduled visit post baseline	Targeted study day	Analysis window in study days
Week 1 (Visit 3A)	8	2 to 46
Week 12 (Visit 4)	85	47 to 127
Week 24 (Visit 5 – EOT)	169	128 to 211
Week 36 (Visit 6 – EOS)	253	≥212

Study days are calculated considering Day 1 as the day of first administration of intervention.

Table 11 - Analyses window definition for participants assigned to PK - Schedule B

Scheduled visit post baseline	Targeted study day	Analysis window in study days
Week 2 (Visit 3B)	15	2 to 50
Week 12 (Visit 4)	85	51 to 127
Week 24 (Visit 5 – EOT)	169	128 to 211
Week 36 (Visit 6 – EOS)	253	≥212

Study days are calculated considering Day 1 as the day of first administration of intervention.

Table 12 - Analyses window definition for participants following the Schedule of Activities from initial version of the protocol dated of 30-Mar-2022

Scheduled visit post baseline	Targeted study day	Analysis window in study days
Week 1 (Visit 3)	8	2 to 11
Week 2 (Visit 4)	15	12 to 22
Week 4 (Visit 5)	29	23 to day 57
Week 12 (Visit 6)	85	58 to day 127
Week 24 (Visit 7 – EOT)	169	128 to 211
Week 36 (Visit 8 – EOS)	253	≥212

Study days are calculated considering Day 1 as the day of first administration of intervention.

Unscheduled visits

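### A Visit 6 held 4 or 5 days early, inside its permitted window, sets the Week 36 ISS7, HSS7 and mUAS7 to missing even with a complete diary

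*SAP*

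**What the plan says.** Four rules meet at the end-of-study visit.

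- **Scoring week.** SAP 3.3.1.2: "For subsequent visits, the sum of the 7 measurements on and prior to the target visit will be used". Its worked example is the "sum of days 163 through 169 for the visit at Week 24". It continues: "Day ranges to be used for ISS7 and HSS7 derivations from Week 1 to Week 36 are described in" SAP 5.6, where Table 13 gives Week 36 as Days 247-253 with target Day 253.
- **Diary period.** The schedule of activities in Protocol 1.3 has the modified UAS7 completed "once daily from Visit 1 to Visit 6". Visit 6 is the end-of-study visit.
- **Visit window.** Footnote a of the same schedule: "Allowed time window of ± 3 days for each visit of treatment period and ± 5 days for the Follow-up visit". SAP 5.4 places Week 36 at Day 253: "Study days are calculated considering Day 1 as the day of first administration of intervention".
- **Missing days.** SAP 3.3.1.2 requires more than half of the daily scores ("i.e. 4 or more non-missing scores) then the weekly score will be calculated as the sum of the available scores divided by the number of" those scores, times 7). With fewer than 4 the weekly score is missing, and mUAS7 is missing whenever ISS7 or HSS7 is.

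The same SAP section plans by-timepoint summaries of ISS7 and HSS7 from baseline to end of study, and of mUAS7 by timepoint.

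**The concern.** The Week 36 range ends on a fixed calendar day, but diary collection ends on the day of the visit. When a permitted visit comes before Day 253, the last days of the range can never be filled. If enough are lost, the 4-of-7 rule treats the child as if the diary had not been kept. The cause would be scheduling, with no lapse in compliance.

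At stake is the last planned summary of urticaria activity in follow-up. SAP 4 records that enrollment stopped after 15 participants, and SAP 3.1 reports results overall and in four intervention groups. One or two missing values would show in a group's row.

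**Working it through.** **Inputs.** Week 36 range and target day: SAP Table 13. Last diary day: Visit 6, Protocol 1.3. Window of 5 days either side: Protocol 1.3, footnote a. Minimum of 4 daily scores: SAP 3.3.1.2.

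**Reproducing Table 13.** Target day = 7 × week + 1; range = target − 6 to target.

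- Week 24: 7 × 24 + 1 = 169, range 163-169
- Week 35: 7 × 35 + 1 = 246, range 240-246
- Week 36: 7 × 36 + 1 = 253, range 247-253

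All three match the table, so the range ends on the target day and does not move with the actual visit.

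**Permitted Visit 6 days**, counted from Day 253: 253 − 5 = 248 to 253 + 5 = 258.

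**Diary days left in the range** for a visit on Day V with a complete diary: min(V, 253) − 246 if an entry is made on the visit day, and min(V − 1, 253) − 246 if not.

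| Visit 6 on Day | Visit-day entry made | Not made |
|---|---|---|
| 248 | 2, missing | 1, missing |
| 249 | 3, missing | 2, missing |
| 250 | 4, prorated | 3, missing |
| 251 | 5, prorated | 4, prorated |
| 252 | 6, prorated | 5, prorated |
| 253 | 7, full | 6, prorated |
| 254-258 | 7, full | 7, full |

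The score is lost on 2 of the 11 permitted days, or on 3 of 11 without a visit-day entry.

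**Week 24.** Visit 5 may be as early as Day 169 − 3 = 166, but the diary continues to Visit 6. Days 163-169 can all be recorded, so the secondary endpoints are not exposed.

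**Other visit windows.** SAP Tables 10-12 assign Day 212 onward to Week 36, but only as a default where nothing else is stated. Table 13 is the specific rule for these scores, so the wider window does not restore them.

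**Sensitivity to the anchor.** The documents do not say whether the 5 days are counted from Day 253 or from the actual Visit 5. If from a Visit 5 on Day 166, Visit 6 could fall on Day 166 + 84 − 5 = 245, and every visit on Days 245-249 would lose the score.

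**After the fix.** A Day 248 visit uses Days 242-248 and a Day 249 visit uses Days 243-249. Each has 7 of 7 scores, or 6 of 7 without a visit-day entry. The overlap with Week 35 (Days 240-246) is 5 days (242-246) and 4 days (243-246) respectively.

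**The case against.** The strongest reply is that this is an edge case at a timepoint that carries no endpoint. ISS7, HSS7 and mUAS7 are secondary endpoints at Week 24 only. Efficacy is descriptive with no estimands, and follow-up data collected after the primary lock go to an addendum to the study report. Fixed weeks also have a merit: the 36 weekly scores do not overlap and cover the same study days in every child. All of this stands, and it sets the size of the point.

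A reader might infer that any early end-of-study visit loses the score. The 4-of-7 rule prevents that: visits on Days 251 and 252 still give a prorated score, as does Day 250 when the visit-day entry is made.

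A reader might also infer that the off-treatment picture is lost. It is not. Table 13 scores every week, and Week 35 remains complete for a Day 248 visit, with only Days 247-248 unused. The last planned dose is at Week 20 or Week 22 (Protocol 1.3, footnote f), so Week 35 is already 13 to 15 weeks after it.

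One could argue that the SAP sentence on the target visit already means the actual visit. The worked example and Table 13 both end on the target day, so that reading would contradict them.

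**Conclusion.** The point holds in a narrow form. With the window counted from Day 253, a compliant child seen on Day 248 or 249 (also Day 250 without a visit-day entry) has no Week 36 ISS7, HSS7 or mUAS7 despite a complete diary. The consequence is confined to the descriptive end-of-study summary. It is a minor point, worth correcting because the data exist and the planned summary is small.

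The number of children affected cannot be derived from the documents. Spreading visits evenly over the 11 days would give 15 × 2/11 = 2.7 to 15 × 3/11 = 4.1 children. A reader might take that as an estimate, but the documents give no distribution of visit days and do not show that all 15 children reach Visit 6. If visits fall close to Day 253, the number is zero. The actual Visit 6 dates settle it.

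**What to change.** In SAP 3.3.1.2 and as a note to Table 13, state that when Visit 6 occurs before Day 253 but within its permitted window, the Week 36 (end-of-study) score uses the 7 calendar days ending on the Visit 6 date, for example Days 242-248 for a Day 248 visit. In all other cases Days 247-253 apply. The 4-of-7 rule is unchanged.

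The range should be tied to the visit date and not to the last entry made. Otherwise a child who stopped the diary early would have the range moved back to suit, which would weaken the 4-of-7 rule. The same note should say that the window is counted from Day 253, since the documents leave this open.

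The cost is a sentence in the SAP and a small programming change. The drawback belongs in a table footnote: for early visits the end-of-study week shifts by up to 5 days (253 − 248) and shares up to 5 days with the Week 35 range, so those two scores are not independent in those children.
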